The proposed study is a longitudinal (9-month) RCT in which primary caregiver parents (as defined in inclusion criteria) of technology-dependent children will be randomly assigned to one of two study arms: (1) The **Attention Control arm** will receive weekly phone calls for the first 4 weeks and at 2 and 4 months post-enrollment plus the current standard of care, whereby caregivers phone their healthcare providers when they have questions or concerns; and (2) The **Resourcefulness Training[©] arm** will receive (a) individually tailored instruction on personal and social resourcefulness skills via the Resourcefulness Video and interventionist, (b) instruction for the online log-writing (via REDCap) so for the parent to describe resourcefulness application, (c) access to the study website with videotape vignettes and Resourcefulness Video, and (d) boosters at 2 and 4 months post-enrollment that will include reinforcement of skills learned and additional online log writing. Measures of parents' outcomes (mental and physical HRQoL, depressive cognitions, depressive symptoms, appraised stress, and burden) and self-management behaviors (appraised/objective sleep, positive health practices) will be obtained at enrollment (T1), then 6 weeks (T2), 3 months (T3), 6 months (T4), and 9 months (T5) post-enrollment to analyze the immediate, extended, and long-term effects of the intervention on parents' outcomes. Chronic stress will be measured by obtaining parents' hair cortisol levels and objective sleep by actigraphy at T1, T3, T4, and T5 to examine changes over time. We will also obtain measures of the mediating (personal and social resourcefulness) variable and covariates (caregiver's race/ethnicity, gender, family income, duration of caregiving, child's functional status, and type of technology).

Research Procedures. The Project Director will notify the data collector of potential participants. He/she will schedule an appointment at a mutually agreed upon time and in a private place of the parent's choosing (e.g., parent's home, library). At that meeting, the data collector will have the parent read the consent form and answer any questions. After written, informed consent is obtained, the data collector will collect baseline (T1) data (questionnaires),

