and afterwards collect a hair sample (at the place of the data collection visit) for hair cortisol analysis from the vertex of the parent's head using a standardized protocol.⁹⁰ Next, the data collector will instruct the parent regarding the Actiwatch (Philips Respironics, Bend, OR) protocol to measure sleep patterns. This includes application of the Actiwatch on the non-dominant wrist during the enrollment visit with instructions to wear it continuously for 10 days in order to capture baseline sleep patterns. Parents will also receive instructions on a sleep history booklet that will supplement Actiwatch actigraphy data during sleep pattern analysis (e.g., reason for night awakenings). Following data collection, the Project Director will log into a secured database and receive the subject's randomly assigned study arm (Attention Control or Resourcefulness Training). Data collectors will be blinded to all participants' study arm assignment. Randomization will be performed using Minim,⁹¹ a computer minimization stratified randomization program. Minimization helps achieve balance in treatment assignment within strata for targeted covariates.⁹² Stratification variables are sex (female, male), race/ethnicity (White non-Hispanic, all others), and OTA³² group (mechanical ventilator, intravenous nutrition/medication, or respiratory/nutritional support). In keeping with the good clinical practice policy (NOT-OD-16-148), the PI will ensure that all key personnel and staff obtain the Good Clinical Practice Training. The Graduate Student RA will keep a list in our NIH Regulatory Binder.

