Attention Control arm. The Attention Control arm will receive study attention via in-person contact at T1, T3-5, weekly phone calls from the Project Director (2-4 minutes) for the first 4 weeks, then phone calls at 2 and 4 months after enrollment to maintain consistency with the intervention arm. The Project Director will ask parents to describe how they/their child are doing. These calls will help to build a relationship with subjects to promote study retention. We recognize that in this group parents may obtain self-initiated caregiving information and support, which will vary among this group. We will use the Information and Support Form to monitor their acquisition of information and support at 6 weeks, 3 months, 6 months, and 9 months post-enrollment. While usual care may vary depending on the healthcare providers seen, all parents assigned to this group can call a physician or nurse to ask specific questions as needed.

Resourcefulness Training Intervention[®] arm. After we collect T1 data, the interventionist will schedule an appointment to conduct the initial instruction for the RTI[®] during a session lasting approximately 1 hour either face-to-face in a private place of the parent's choosing or via Zoom using a computer, tablet or smart phone. The interventionist will also conduct all intervention arm follow up.

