to non-compliance.¹⁰⁷ They will be asked to think of a place to keep the sleep history booklet that will serve as a reminder. Participants will be mailed a \$5 gift card each time they return the Actiwatch and sleep history booklet to the study office (baseline and 3month, 6 months, 9 months post baseline).

Follow-Up Contacts and Data Collection. Data will be collected for both study arms via mailed questionnaires, emailed link to REDCap surveys (depending on participant preference) at approximately 6 weeks (T2) after the initial delivery of the Resourcefulness Training Intervention or enrollment for the control group. Reminder phone calls will be made by data collectors if questionnaires are not completed within 2 weeks. Data collectors will obtain data about informational, social, caregiving support they may have received related to care of the technology-dependent children at (e.g., phone calls to healthcare providers, amount and type of Internet usage to obtain information, social support or lay caregiving, home nursing) using the Information and Support Form by phone at T2 and in person T3-T5 (3, 6, 9 months post-enrollment). Data collectors will also meet with parents face-to-face at T3-T5 to collect questionnaire data, obtain hair samples, and reapply the Actiwatch and will be blinded to group assignment. Table 2 details timing for all measures. In addition, the interventionist will phone the intervention arm subjects weekly for the first 4 weeks post-enrollment for the initial intervention and at 2 and 4 months post-enrollment for the booster sessions. To maintain consistency of contact with the intervention group, the Attention Control arm will receive weekly phone calls from the Project Director for the first 4 weeks post-enrollment, and then at 2 and 4 months after enrollment. We will also invite eligible intervention arm participants to complete the Intervention Exit Survey (see section Intervention Exit Survey above). If a parent asks a question about the care of their children, they will be referred to their healthcare provider.

Technology-Dependent Child Death. If a technology-dependent child dies during the study period, the Project Manager will send a condolence card to the family and obtain descriptive data about the date and cause of the child's death in the Electronic Medical Record. Data regarding the technology-dependent child's death will not be collected by ACH staff.

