Children Who No Longer Require Technology. Parents whose children no longer require medical technology will remain in the study, and their data will be analyzed separately.⁴¹ We will document how soon after study enrollment the technology was discontinued. We expect about 5% will have technology discontinued and thus we will enroll additional participants to compensate for this attrition.

Retention Plans. To maximize retention over the 9 months, we will send birthday cards on the parent's and child's birthdays, as well as bi-monthly postcards with an inspirational message and contact information for the study office. Furthermore, we will recruit data collectors who are experienced and comfortable working with families who have children with special needs.

Controlling diffusion of intervention approaches. In our prior work, we found that few participants knew one another, so we believe the threat of diffusion is low. We recognize the possibility of the Hawthorne effect impacting our data. Therefore, the research team believes that it is vital to reliably track the amount of information and emotional support obtained by parents in all study arms and expect that any Hawthorne effect will be equally distributed because we are collecting the same information for both arms.

Measures. Study measures will be obtained at baseline (study enrollment), 6 weeks, and 3, 6, and 9 months post-enrollment, time frames selected based on prior work with caregivers and RTI[®] in order to capture variability over time. Table 2 shows study measures and measurement points. We chose measures based on our prior work with caregivers that are psychometrically sound and/or recommended by NIH as common data elements to facilitate cross-study analysis and increase the scientific impact of our study analyses.

Parent Outcome Variables: Parent Mental and Physical HRQoL will be measured by the 10-item Patient-Reported Outcomes Measurement Information System (PROMIS[®]) Short Form v.

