Aims 1 & 3: Analysis of the monthly rate of change for each parent outcome in each arm will be estimated via linear mixed models and fit using SAS PROC MIXED.^{128,129} Each model will include a random intercept and slope (possibly modeled using a polynomial spline) to account for between-subject variance in each outcome over time. Conditional on these random effects, we will explore within-subject variance in each outcome over time using different residual covariance structures and select the most appropriate structure using likelihood-based criteria. Fixed effects will include a continuous variable to represent time since randomization, an indicator variable to represent the intervention, and stratification factors used during randomization (facility, OTA technology group, race/ethnicity). Assuming a linear rate of change over time, the regression coefficient of the terms representing interactions between time and the intervention indicator variable will be used to estimate the difference in the monthly rate of change in each outcome between arms.

Aim 2 & 4: To determine if resourcefulness mediates the effect of the RTI[©] on parent outcomes (psychological and physical health, self-management behaviors), a theory-based causal mediation model^{130,131} will be fit using separate linear mixed models of parent outcomes at 3 months after randomization that adjust for the intervention indicator variable, stratification factors, and the mediator at 6 weeks after randomization. This model will allow us to decompose the total effect of the RTI on parental outcomes at 3 months into direct and indirect (or mediated) effects and estimate the proportion of the total effect that is mediated. Variance estimates and 95% confidence intervals will be estimated using a bootstrapping procedure based on 1000 bootstrap samples. To more fully explore the temporal pattern of mediated effects, we will use similar models to estimate the mediated effect using measurements of the mediator and parental outcome taken at other time points as well (e.g., total effect of RTI[©] on parent outcomes at 6 months that are mediated by personal and/or social resourcefulness at 3 months).

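### The documents give conflicting starting points for the 6-week assessment (T2); the data-collection text counts from training in one arm and from enrollment in the other

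*Combined protocol and SAP*

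**What the plan says.** The combined protocol and SAP describes the timing of T2 in five places.

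- **Follow-Up Contacts and Data Collection:** T2 is at approximately 6 weeks "after the initial delivery of the Resourcefulness Training Intervention or enrollment for the control group". In the same section, T3 to T5 are counted from enrollment.
- **Study design paragraph:** measures are taken at enrollment, "then 6 weeks (T2), 3 months (T3), 6 months (T4), and 9 months (T5) post-enrollment", with no distinction by arm.
- **Measures:** "Study measures will be obtained at baseline (study enrollment), 6 weeks, and 3, 6, and 9 months post-enrollment".
- **Primary Analyses, Aims 2 and 4:** the lead mediation model relates outcomes at 3 months to "the mediator at 6 weeks after randomization".
- **Opening purpose statement:** the 6-week, 3-, 6- and 9-month outcomes are counted from the intervention.

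Two further statements fix the order of events. Research Procedures says: "Following data collection, the Project Director will log into a secured database and receive the subject's randomly assigned study arm". The section on the Resourcefulness Training Intervention (RTI) arm says: "After we collect T1 data, the interventionist will schedule an appointment to conduct the initial instruction". No maximum delay to that appointment is given, and no T2 visit window.

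**The concern.** The control arm has no event that corresponds to the training session. If T2 is counted from training in one arm and from enrollment in the other, the two arms are measured at different times since randomization unless training takes place on the day of enrollment. The offset can run in one direction only: T2 is later in the RTI arm.

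Two uses of T2 are exposed. The first is any direct comparison of the arms at 6 weeks. The second is the lead mediation model for Aims 2 and 4, which takes resourcefulness at T2 as mediator and the parent outcome at T3. That model adjusts for arm, stratification factors and the mediator, and has no term for time. Change in resourcefulness over the extra days would be counted as part of the effect of arm on the mediator, and the interval from mediator to outcome would differ by arm. The split into direct and indirect effects would then partly reflect the assessment schedule. The planned sensitivity analysis for sequential ignorability deals with unmeasured confounders, not with measurement timing.

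**Working it through.** **Inputs from the documents.** T2 is at 6 weeks (42 days). T3 is at 3 months, taken here as 13 weeks (91 days) from enrollment. Arm assignment follows T1 data collection, and RTI is delivered at a later appointment.

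**Input that must be assumed.** The lag L from enrollment to RTI delivery is not stated. I use 1 to 2 weeks as an illustration. The plan has no figure of its own for the offset, so there is nothing to reproduce. The sample size (144 for the power calculation, 210 enrolled) and the 0.025 significance level do not depend on T2 timing.

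**Step 1: day of T2 under the data-collection text.** Control: 42. RTI: 42 + L.

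**Step 2: T2-to-T3 interval, with T3 on the enrollment clock.** Control: 91 − 42 = 49 days. RTI: 91 − 42 − L.

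| Assumed L | T2 day, RTI | T2 day, control | T2–T3, RTI | T2–T3, control | Shortening |
|---|---|---|---|---|---|
| 0 days | 42 | 42 | 49 | 49 | 0 |
| 7 days | 49 | 42 | 42 | 49 | 7/49 = 14% |
| 14 days | 56 | 42 | 35 | 49 | 14/49 = 29% |

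**Step 3: if the purpose statement governs every visit in the RTI arm.** T3 moves to day 91 + L, so the T2–T3 interval is 49 days in both arms. T2 is still L days later after randomization in the RTI arm. The unequal interval therefore depends on T3 staying on the enrollment clock; the unequal time since randomization does not.

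**Step 4: Aims 1 and 3.** The mixed model uses continuous time since randomization. With actual dates, a linear trend shared by both arms causes no bias. The plan does not say whether actual or nominal times are used, so I checked nominal coding with simple least-squares slope weights.

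- Times in months: 0, 1.38, 3, 6, 9. Mean 3.876; sum of squared deviations 52.79.
- Weight at T2: (1.380 − 3.876)/52.79 = −0.0473 per month.
- One week is 0.23 months. Bias in the slope difference per week of lag: −0.0473 × 0.23 = −0.0109, about −1.1% of the common monthly trend. At two weeks it is about −2.2%.

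**Step 5: other mediation pairs.** The plan also names the 3-month mediator with the 6-month outcome. With T3 and T4 counted from enrollment in both arms, that pair is unaffected.

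**Step 6: effect of a common anchor.** With T2 timed from randomization in both arms, T2 is day 42 and the interval to T3 is 49 days in each, so the difference is 0. T2 then falls 42 − L days after training. The log period lasts 28 days, so T2 precedes its end when 42 − L < 28, that is, when L > 14 days.

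**The case against.** The strongest reply is that this may be loose wording with a small effect. The documents use enrollment and intervention almost interchangeably. The weekly calls are placed after training in one section and after enrollment in another, and the boosters are described both ways. Either the authors treat the two dates as one or they expect a short lag. T2 is also only approximate: it is done by mail or emailed link, with reminder calls after 2 weeks, so dates will scatter in both arms anyway. Timing T2 from training could also be deliberate, so that it falls at a fixed time after training, although the plan gives no such reason.

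Much of this stands. The size of the lag is unknown, and a one-week offset may lie within the ordinary scatter. It would still be systematic by arm, which scatter common to both arms is not.

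A reader might infer more than the documents support:

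- **That T2 is certain to be measured at different times in the two arms.** Only one section says so directly. Others give a common anchor, so this is a contradiction and not an established design.
- **That the lag is at least 10 days because of the baseline Actiwatch wear.** Nothing says that training waits for the device.
- **That all drift since enrollment becomes an arm difference.** Only change over the extra days does, between day 42 and the later T2.
- **That the main longitudinal results are compromised.** Step 4 shows little effect on Aims 1 and 3.

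**Conclusion.** The point holds as a contradiction over the T2 anchor, with a limited but real consequence. If the data-collection text is followed, T2 is later in the RTI arm by the unstated lag. The illustrative figures (day 49 to 56 against 42, and 42 to 35 days to T3 against 49) rest on an assumed lag of 1 to 2 weeks and on T3 staying on the enrollment clock. The offset is zero if training takes place on the day of enrollment.

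The exposure is confined to direct 6-week comparisons and to Aim 2 and 4 models that use T2. The documents give no rate of change in resourcefulness over the lag, so the resulting bias in the mediated effect cannot be quantified. Sample size and significance level are unaffected. It should be corrected, because the affected model is the first one specified for the mediation aims and the correction is cheap.

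**What to change.** 1. Time T2 from randomization/enrollment in both arms, with one common visit window. Reconcile the purpose statement, the study design paragraph, Follow-Up Contacts and Data Collection, Measures, and the Aims 2 and 4 text.
2. State that the mixed models for Aims 1 and 3 use actual assessment dates, as time since randomization.
3. Record days from randomization to RTI delivery and to T2, and report them by arm.
4. For parents already assessed, check the mediation result in one of two ways: restrict to T2 assessments within a common window from randomization, or use the planned 3-month mediator with the 6-month outcome. The restriction selects on a post-randomization date, so treat it as a sensitivity analysis only.
5. Do not adjust the mediation models for days to T2. Under the data-collection text that variable is post-randomization and largely determined by arm, so it could absorb the effect being decomposed.

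The cost is a few sentences, a changed T2 mailing date in the RTI arm, and two recorded intervals. The downside is that T2 falls somewhat sooner after training. If the lag exceeds about 2 weeks, T2 would come before the 4-week log period ends, which is a further reason to report the lag.

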1.	Parent primary caregiver (biological, adoptive, or foster mother, father, grandmother or grandfather) for a technology-dependent child based on the Office of Technology Assessment (OTA) classification criteria ³² (Group 1, mechanical ventilators; Group 2, intravenous nutrition/medication; Group 3, respiratory or nutritional support). For children with more than one type of technology, we will follow OTA guidelines for classification.
2.	At least 18 years of age up to 80 years old
3.	Able to speak and understand English
4.	The technology-dependent child must be 17. 4 years or younger and receive care in the home from his/her parent

***For the Intervention Exit Interview- We will include all the above inclusion criteria 1-4 but will add the following:

5. Subjects who were randomly assigned to the Intervention Arm and completed the Resourcefulness Training[©] session with the interventionist and completed Time 5 data collection.

Exclusion Criteria	
1.	Parents of children with a cancer diagnosis due to the short term use of technology following initial diagnosis and treatment

***For the Intervention Exit Interview- We will include the above exclusion criteria 1 but will add the following:

2. Subjects who were randomly assigned to the Attention Control arm.

We will enroll 100 subjects for this study at UHCMC, 50 subjects from Akron Children's Hospital and 60 subjects from Cleveland Clinic for a total number of 210 subjects.

We will exclude illiterate or non-English speaking individuals due to the amount of reading, writing that must be done as part of the intervention and follow up data collection. Also, our instruments have not been translated into another language.

We will include pregnant women or women who become pregnant while enrolled in the study because many mothers of technology-dependent children are in the child-bearing years. They will be told that they are volunteers and can leave the study at any time.

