Hospital telehealth visits a message is sent to the physician through Epic letting them know their patient has been prescreened as a potential candidate for the study. At the conclusion of the visit the physician then asks the parent if they are willing to hear about a research study that is examining ways to decrease stress in parents caring for a child dependent on technology. If they agree the physician will forward the link to the telehealth visit to the Akron nursing research team member after their portion of the visit is finished (link to the visit is sent in a secure chat feature in Epic when it is nurse research team member's turn to talk). The Study Information letter is reviewed with the caregiver and any of their questions are answered. If the caregiver agrees to have information shared with CWRU, the nursing research team member collects their contact information, writes it on the sheet including the team member name and date it was collected and checks the box indicating it was information collected during a telehealth visit. The study coordinator from Akron Children's Hospital (ACH) will send the name, address, phone number, (best time to contact) of potential study participants' who have agreed to be contacted by the CWRU study team for possible study enrollment via secure email to the CWRU Project Manager. The CWRU research team would then phone the potential participant to give more information about the study and answer any questions they may have. If interested in enrolling in the study, the CWRU research team member will schedule an appointment with the potential participant to obtain informed consent, consent to have the technology dependent child's information (i.e., ER visits, hospitalizations during parent's enrollment in the study) released to [name] and the study team and data collection. CWRU research team will send the parent's completed and signed release of information form to ACH Study Coordinator via secure email. CWRU team will provide set up, training plus meet with the ACH Study Coordinator and recruiting team on recruitment protocols. ACH Study Coordinator will schedule at least monthly teleconference to discuss progress on recruitment goals (approximately 44 potential participants). ACH Study Coordinator to send the CWRU research team the number of ER visits and number and length of hospitalizations for the technology-dependent children of enrolled study participants after a completed, signed release of information form is received.

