
An appointment will be made to meet with the potential participant at the time and private place of their choosing (that has an area or nook for a private discussion with no outside person within hearing distance of the conversation e.g., their home, public library, their place of employment, child's therapy center such as United Cerebral Palsy Center, Dahm's Clinical Research Unit) to obtain informed consent and collect data. The hair sample will be collected in a private place of the parent's choosing. Study personnel will obtain informed consent and explain to the potential participant that he/she is being asked to provide consent for participation in a research study. It will be explained that participation is totally voluntary and their choice regarding participation will not affect their child's care in any way. Additionally, parents will be given a description of the study, procedures, risks and benefits, confidentiality and voluntary nature of the study including the option to withdraw at any time. Following this discussion, parents will be given the consent form to review. Parents will be given the opportunity to take a few minutes alone to review the written consent form and to make a decision regarding participation. Parents will be assured that none of the data obtained will be communicated to any healthcare personnel at the outpatient clinic or hospital site.

The RB&C Specialty Clinics (Pulmonary, Gastroenterology, Trach/Vent, Comprehensive Care, Aerodigestive) will identify names and contact information of patients meeting inclusion criteria. We will also screen patients being seen in the above clinics using EMR.

There are approximately 180 potential participants at UH and approximately 150 potential participants at Cleveland Clinic who have not been enrolled in one of the investigators previous studies with approximately 15-20 new candidates at each site per year. Akron Children's Hospital has over 250 potential participants and will recruit at least 44 potential participants.

We will conduct the research data collection at a private place of the parent's choosing such as their home, library, place of employment, or restaurant. Our study office is located in the FPB School of Nursing, CWRU.

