Data and safety monitoring will be conducted to determine if data collection should be altered or stopped. Every 6 months the DSM Committee will assess the risks and benefits of the study by reviewing individual adverse events and unanticipated problems that have occurred during the study. The committee members are not part of the research team. This committee will review data on this study regarding 1) study safety, including auditing selected cases for compliance with IRB requirements, conformance with informed consent requirements, verification of source documents, and investigator compliance; 2) minimizing research-associated risk; and 3) protecting the confidentiality of participant data. In addition, it will review (1) all causes of mortality and (2) issues with participation. The rate of recruitment refusal (percent and reasons) and subject

attrition (percent and reasons) will be tracked and reported at these reviews. Differential attrition from the intervention and control arms also will be monitored. Written reports will be developed and submitted to the committee by the CWRU PI, [name], the principal investigator will make the decision related to altering the study in collaboration with the committee if more than two mothers/fathers experience significant discomfort or distress that required a referral to United Way First Call. [name] will be responsible to submit written reports to any funding agency within 2 weeks of the meeting. If concerns or problems are identified by the SMC, they will be reported to the IRB and funding agency via email by [name] within 3 business days after they are identified. If there are recommendations made by the SMC, the action plan for response or notice of any actions taken by the IRB regarding the research and any responses to those actions will be provided to Funding Agency Officials within 2 weeks.

References

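### No source is stated for the date and cause of an Akron child's death (nor is study-team record access at Cleveland Clinic), and at every site Aim 6 has no time-at-risk term or rule for death

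*Combined protocol and SAP*

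**What the plan says.** Under Technology-Dependent Child Death, the Project Manager is to "obtain descriptive data about the date and cause of the child's death in the Electronic Medical Record". No site limit is given. The next sentence says that data on the child's "death will not be collected by ACH staff". The Akron recruitment text places the Project Manager on the CWRU team.

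That same text describes what the study receives from Akron. The parent signs a release for the child's emergency visits and hospitalizations while the parent is enrolled, after which the plan has the "ACH Study Coordinator to send the CWRU research team the number of ER visits and number and length of hospitalizations". Death is not listed. The recruitment sections name the record systems that the study team uses, for screening, and a later summary of recruitment describes them as UH systems.

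Planned enrolment is 100 at UHCMC, with "50 subjects from Akron Children's Hospital and 60 subjects from Cleveland Clinic for a total number of 210 subjects". Elsewhere Akron "will recruit at least 44 potential participants".

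On the safety committee, the fuller of the two data and safety monitoring descriptions says "it will review (1) all causes of mortality and (2) issues with participation". It also has attrition, with reasons, reported at each six-monthly review and compared between arms.

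In the analysis section, Aim 6 compares the rate of emergency visits and hospital days over nine months by Poisson regression, adjusted for arm and covariates. It mentions neither an exposure term nor what happens when a child dies.

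**The concern.** Two things are at stake, and they are best kept apart.

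The first is safety reporting. A committee that reviews causes of death needs a source for them. The plan gives the task to one person on the CWRU team, rules out help from Akron staff, and describes an Akron data feed that does not include death. If the committee's remit covers the children, its review could be complete at one hospital and incomplete at the others.

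The second is Aim 6. A child who dies stops accruing visits and hospital days. If that truncated count is set against a full nine months, the child's rate is understated and a death can look like reduced use. The plan elsewhere expects the intervention to lower emergency visits and hospitalizations, so this error would run in the hoped-for direction if deaths were more frequent, or earlier, in the intervention arm.

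**Working it through.** **1. Site shares.** The enrolment paragraph gives 100 + 50 + 60 = 210, which reproduces the stated total. One child per enrolled parent is assumed.

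- Akron: 50/210 = 23.8% (44/210 = 21.0% on the lower recruitment figure).
- Cleveland Clinic: 60/210 = 28.6%.
- Both: 110/210 = 52.4%.

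**2. What is stated for a death, item by item.**

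| Item | Stated route | Akron | Cleveland Clinic |
|---|---|---|---|
| Fact of death | Study calls, T2 to T5 contacts, withdrawal, attrition reasons | Available | Available |
| Date and cause | Project Manager, from the medical record | Local staff excluded; release and feed omit death; no record access stated | No record access stated |

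The route for the fact of a death is real. Study staff phone both arms in the first four weeks and at 2 and 4 months, phone again at T2, and meet parents at T3 to T5. The withdrawal paragraph names the child's death as a possible cause of withdrawal, and attrition reasons go to the committee. This route does not secure the date or cause. Parents who withdraw are only invited to give reasons, they are not followed afterwards if they withdrew voluntarily, 20% to 30% attrition is expected by Month 9, and no vital-status field is described.

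**3. How many Akron deaths might be involved.** The documents give no child mortality rate, so nine-month mortality m is an assumption, shown over a range. Expected Akron deaths = 50m; chance of at least one = 1 − (1 − m)^50.

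| m (assumed) | Expected Akron deaths | Chance of at least one |
|---|---|---|
| 1% | 0.5 | 39% |
| 3% | 1.5 | 78% |
| 5% | 2.5 | 92% |
| 10% | 5.0 | 99% |

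These are deaths whose date and cause would lack a stated source. They are not deaths unknown to the study.

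**4. Aim 6, one child.** With Y events before death at month t, the rate over time at risk is Y/t. With no exposure term, the model in effect uses Y/9. The ratio is t/9, whatever the child's use before death. For illustration, at t = 2 the rate is understated by 1 − 2/9 = 77.8%.

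**5. Aim 6, whole trial.** If deaths fall mid-follow-up on average, each removes half of that child's person-time.

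- Akron deaths only: (50/210) × m/2 = 0.12% at m = 1%, and 1.19% at m = 10%.
- Deaths at all sites: m/2 = 0.5% at m = 1%, and 5% at m = 10%.

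Suppose the event rate is the same before death as in other children, and let s₁ and s₀ be the shares of person-time lost in the two arms. The uncorrected rate ratio is then the true ratio × (1 − s₁)/(1 − s₀). It is distorted only so far as s₁ and s₀ differ, and the documents give no reason to expect that they will.

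**The case against.** The strongest reply is that the two sentences on child death simply divide the work: CWRU collects and Akron staff do not. On that reading the exclusion is not a gap. The screening systems named in the recruitment sections need not define the medical record meant in the death section. The committee text does not say whose mortality is meant, and the enrolled subjects are parents. For Aim 6, the Akron release already confines the counts to the parent's enrolment.

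Much of this stands. A reader might infer that Akron deaths have no way of reaching the committee, or that all of them would go unrecorded. The documents do not support that: collection is assigned for every child, and contacts, withdrawal and attrition reasons can carry the fact of a death from any site. A reader might also infer that the Akron exclusion is what biases Aim 6. It is not. The model states no time at risk at any site, so a perfect Akron date would change nothing in the analysis as written.

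What the reply leaves open is narrower. Dividing the work still needs a source, and none is stated for Akron, nor is record access at Cleveland Clinic. The only deaths for which the plan collects a cause are the children's, so reading the committee's remit to include them is natural, though it remains an inference. Confining counts to enrolment shortens the count without shortening the exposure, which is the Aim 6 fault itself.

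**Conclusion.** The concern holds in this limited form. For Akron children (50/210, 24%) the plan states no source for the date and cause of death. Study-team record access is equally unstated for Cleveland Clinic, which brings the share to 110/210 (52%). If the committee's mortality review is meant to cover the children, it may be incomplete by site as to date and cause, though not necessarily as to the fact of death.

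The Aim 6 fault is separate and trial-wide. Its expected numerical effect is small: about 0.1% to 1.2% of person-time for Akron deaths, or 0.5% to 5% for deaths at all sites, if nine-month mortality is 1% to 10% and deaths fall mid-follow-up on average. Both are assumptions. The 78% figure describes one hypothetical child and is not a trial-level bias. Completeness of safety reporting is the main reason to act, and the low cost of the remedy makes it worth doing.

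**What to change.** 1. **Vital status.** Have the CWRU team record vital status and date of death for every child, at all sites, on contacts it already makes (T2 to T5, study calls, withdrawal). No Akron staff action is needed. Where a parent gives no information, record the last date the child was known to be alive.
2. **Committee reports.** Report child deaths by arm at each six-monthly review.
3. **Reconcile the text.** The Akron data-transfer text, the child-death section and the committee's remit should agree. Either name a source for cause of death that works at every site (parent report is one example), or state whose mortality the committee reviews and in what detail. The date field alone does not settle cause.
4. **Aim 6.** Include log time at risk as an offset, ending at the child's death or the end of observation, for all sites.

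The cost is one added form field, a line in the committee report, a sentence in the analysis section and a minor amendment.
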